***At week 260 or end of study visit***

**Progression of Disease (PD)** will be defined as a  $\geq 25\%$  increase on the 12 month MRI in the sum of the product of the biperpendicular diameters of enhancing disease; or new lesions; or substantial worsened T2/FLAIR; or significant clinical neurological decline unexplained by a change in medication or concurrent comorbidities. The SPD is the sum of the products of biperpendicular diameters of the measurable enhancing lesions (max 5 lesions)

**Complete Response (CR)** will be defined as the disappearance on the month 12 MRI or CT scan of all enhancing disease, no new lesions, with stable or improved T2/FLAIR; no more than physiological steroids; clinically stable or improved

**Partial Response (PR)** will be defined as a  $\geq 50\%$  decrease on the month 12 MRI or CT scan in the sum of the products of the biperpendicular diameters of enhancing disease, no new lesions, stable or improved T2/FLAIR, stable ( $>2$  months) or decreased steroid dose, clinically stable or improved

**Stable Disease (SD)** will be defined as a patient who do not qualify for complete response, partial response, or progressive disease, stable or improved T2/FLAIR; stable ( $>2$  months) or decreased steroid dose, clinically stable or improved

**Overall survival (OS)** will be defined as the time from baseline to the date of death from any cause. Follow up times of patients who are lost to follow up will be recorded and censored. The censoring time point (date last known to be alive) will be recorded.

**Objective Response Rate (ORR)** will be defined as the number of patients with CR + PR - divided by the total number of patients at time points 12, and every 12 months thereafter.

**Progression Free Survival (PFS)** will be defined as the time from baseline to documented PD or death from any cause. Patients without event would be censored at the last valid tumor assessment (before starting new anti-cancer therapy) at which they were known to be progression-free.

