### **7.1. Inclusion criteria**

1. Signed informed consent
2. Age  $\geq$  18 years
3. Present with newly diagnosed supratentorial Glioblastoma (GBM) with a tissue diagnosis that has been established following either a surgical resection or biopsy. This includes treatment-naïve - (chemotherapy and radiotherapy)- patients with prior diagnosis of a lower grade astrocytoma that has been upgraded to a histologically verified GBM
4. Karnofsky performance score of 70 or higher
5. Patients entering the study must be on a stable dose of no more than 12 mg (maximum) of Dexamethasone (or equivalent) daily for symptoms related to cerebral edema
6. Will be or is undergoing or has received the standard therapy of chemo radiation therapy (60Gy in 30 fractions of 2Gy/day or as per local protocol with concurrent temozolomide of 75mg/m^2 per day PO or as per local practise) no more than 21 days ago
7. Has not yet begun but will begin standard monthly temozolomide therapy
8. Patient must have at least 1 formalin fixed paraffin embedded tumor tissue block representative of glioblastoma available for biomarker analysis and determination of MGMT status (if not already done). If tumor block is not available or not of adequate quality, sufficient pathology material, representative of glioblastoma, must be available
9. Adequate hematological function defined by absolute neutrophil count (ANC)  $\geq$  1.5  $\times$  10^9/L, platelet count  $\geq$  100  $\times$  10^9/L, and hemoglobin  $\geq$  9 g/dL (may have been transfused)
10. Adequate hepatic function defined by a total bilirubin level  $\leq$  1.5  $\times$  the upper limit of normal (ULN) range and AST and ALT levels  $\leq$  2.5  $\times$  ULN for all subjects

11. Adequate renal function defined by an estimated creatinine clearance  $\geq$  30 mL/min according to the Cockcroft-Gault formula (or local institutional standard method)
12. Negative serum pregnancy test at screening for women of childbearing potential

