**Neurological Examination:**

Evaluation of neurological function at each disease assessment will be based purely on the investigator's assessment of the patient's neurological state compared to the neurological function at the time of the last assessment visit. Neurological function must be recorded as Improved, Unchanged, or Worsened.

In the absence of progression based on radiological assessment, patients who clearly neurologically worsen compared to neurological evaluation at the last disease assessment, and whose corticosteroids use is unchanged or increased compared to the previous disease assessment, will be considered to have evidence of disease progression.

**NOTE:** Neurological deterioration independent from the disease being treated should not be considered in the context of the Disease Assessments.

**Corticosteroids use:** at the time of each disease assessment the corticosteroid intake will be compared to corticosteroid intake at the time of the last disease assessment. The changes and dose will be recorded as Increased, Unchanged or Decreased. Increases and decreases in corticosteroid intake should be clinically justified.

**NOTE:** Increases in corticosteroid dose for reasons other than for tumor disease control especially if done to control immune related AE's need to be recorded and taken into consideration when making this comparison.

The corticosteroid dose should be kept stable for 14 days prior to the 12 months MRI or CT scan in order to minimize interference of corticosteroids in the interpretation of response.

**Radiological assessment:** patients who have undergone gross total resection and show neither contrast-enhancing (index lesions) nor non-enhancing lesions (non- index lesions) on MRI or CT scan will be followed for recurrence (the appearance of one or more new lesions). If no signs of progression are observed on the MRI or CT scan, then these patients should have a radiological assessment recorded as "No Change". However, in case of unequivocal evidence of progressive disease (major deterioration in neurological function, and unchanged or increased corticosteroid dose) the Overall Disease Assessment will be "progressive disease". Progressive disease will not need a confirmatory scan.

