1. STATISTICAL STATEMENT AND ANALYTICAL PLAN

1.1. Sample Size Considerations

A convenience sample of thirty (30) patients is based on recruitment feasibility. This sample size will permit estimation of dichotomous outcome rates with margins of error of less than 18% (based on a significance level of 0.05) and estimation of continuous parameter means to within 0.36 standard deviations. This is an early stage study, so analysis will focus on descriptive statistics. Continuous parameters will be summarized by means and 95% confidence intervals or by medians and interquartile ranges, as appropriate. Dichotomous outcomes will be summarized with point estimates of the rate, as well as 95% confidence intervals. Time-to-event data will be summarized using Kaplan-Meier curves.

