1.3.2. Secondary Endpoints

Based on the results of Stupp *et al* (2005) (3), if avelumab had no effect then we would expect to see one-year overall survival and progression-free survival rates of 60% and 27%, respectively. We will conclude that we have preliminary evidence of benefit if either of our observed rates is significantly better based on a one-sided t-test at the 0.2 level of significance. With our projected sample of 30, this corresponds to concluding benefit if at least 21 patients survive to one-year or if at least 11 have survived without progression of disease.

Radiological tumor response will be graded according to the immunotherapy Response Assessment for Neuro-Oncology (iRANO)

Progression of Disease (PD) will be defined as a $\geq 25\%$ increase on the 12 month MRI or CT scan in the sum of the product of the biperpendicular diameters of enhancing disease; or new lesions; or substantial worsened T2/FLAIR; or significant clinical neurological decline unexplained by a change in medication or concurrent comorbidities. The SPD is the sum of the products of biperpendicular diameters of the measurable enhancing lesions (max 5 lesions).

Complete Response (CR) will be defined as the disappearance on the month 12 MRI or CT scan of all enhancing disease, no new lesions, with stable or improved T2/FLAIR; no more than physiological steroids; clinically stable or improved

Partial Response (PR) will be defined as a $\geq 50\%$ decrease on the month 12 MRI or CT scan in the sum of the product of the biperpendicular diameters of enhancing disease, no new lesions, stable or improved T2/FLAIR, stable (>2 months) or decreased steroid dose, clinically stable or improved

Stable Disease (SD) will be defined at 12 months when a patient do not qualify for complete response, partial response, or progressive disease, stable or improved T2/FLAIR; stable (>2 months) or decreased steroid dose, clinically stable or improved

Overall survival (OS) will be defined as the time from baseline to the date of death from any cause.

Objective Response Rate (ORR) will be defined the number of patients with either CR or PR divided by the total number of patients.

Progression Free Survival (PFS) will be defined as the time from baseline to documented PD or death from any cause.

Results will be stratified according to MGMT status, baseline age (>50 yrs), baseline Karnofsky performance score (score of 100), radical tumor resection vs biopsy, primary versus secondary GBM,

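### Objective response rate is divided by all patients, including those with no measurable disease at baseline who cannot respond, so it is diluted by an unknown share

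*Protocol*

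**What the plan says.** ORR is defined three times. Protocol 5.2, under the subheading for week 260 or end of study, has CR plus PR "divided by the total number of patients at time points 12, and every 12 months thereafter". SAP 1.3.2 has "the number of patients with either CR or PR divided by the total number of patients", with no time points, and Protocol 12.3.2 uses the SAP wording. None of the three limits the denominator to patients with measurable disease or says how a patient who died or was not scanned is counted.

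CR is the disappearance of all enhancing disease on the month 12 scan. PR is a decrease of at least 50% in the sum of products of diameters (SPD) of enhancing disease. Neither definition says what happens when the baseline SPD is zero.

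Eligibility (Protocol 7.1) accepts glioblastoma "with a tissue diagnosis that has been established following either a surgical resection or biopsy", and no criterion asks for measurable or enhancing disease. Protocol 9.3.5 foresees patients without it: those with gross total resection who "show neither contrast-enhancing (index lesions) nor non-enhancing lesions (non- index lesions) on MRI or CT scan will be followed for recurrence". If no progression is seen, their radiological assessment is recorded as No Change.

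**The concern.** A response rate is easiest to interpret when every patient in the denominator could in principle respond. Here some may not be able to. A patient who starts with no lesion can stay lesion-free or recur, but has nothing that can shrink by half. Each such patient lowers ORR whatever the drug does, so the figure depends partly on how many lesion-free patients the single center enrols. That makes it hard to set beside a rate from a series with a different surgical mix.

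The CR text leaves a second opening. It does not say that enhancing disease must have been present at baseline, so an analyst working from that sentence alone could score a lesion-free patient as CR, which would push ORR up instead. Finally, three texts for one endpoint should agree, and Protocol 5.2 carries words that the other two lack.

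**Working it through.** **Inputs from the documents.** N = 30 (Protocol 12.1, SAP 1.1). Precision for any dichotomous rate: "margins of error of less than 18% (based on a significance level of 0.05". Expected one-year survival with no drug effect: 60% (Protocol 12.3.2, SAP 1.3.2).

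**Inputs not in the documents, so assumed.** s is the share of the 30 with no measurable enhancing disease at baseline who are never scored CR or PR; the range used is 10% to 60% (3 to 18 patients). p is the response rate among patients with measurable disease; 20% and 30% are used. A count of 3 responders is used for the interval examples. None of these is a forecast.

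**1. The plan's own figure.** The worst-case normal-approximation half-width at a rate of 50% is 1.96 × √(0.25/30) = 0.179. This reproduces the stated bound of under 18%.

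**2. Dilution.** There are 30(1 − s) patients who can respond, and the expected number of responders is 30(1 − s)p. Divided by 30, the reported rate is p(1 − s), and it can never exceed 1 − s.

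| s | Patients who can respond | Highest possible ORR | p = 30% reported as | p = 20% reported as |
|---|---|---|---|---|
| 10% | 27 | 90% | 27% | 18% |
| 20% | 24 | 80% | 24% | 16% |
| 40% | 18 | 60% | 18% | 12% |
| 60% | 12 | 40% | 12% | 8% |

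**3. The same 3 responders on different denominators**, with exact (Clopper-Pearson) 95% intervals:

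- 3/30 = 10.0% (2.1 to 26.5)
- 3/24 = 12.5% (2.7 to 32.4)
- 3/18 = 16.7% (3.6 to 41.4)
- 3/12 = 25.0% (5.5 to 57.2)

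**4. The opposite error.** Suppose lesion-free patients who stay lesion-free were scored CR. Then 3 true responders plus 3, 6 or 9 such patients give 6/30 = 20%, 9/30 = 30% or 12/30 = 40%, against 10% without them.

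**5. The time-point words.** If the extra words in Protocol 5.2 meant patients still alive at month 12, the denominator would be 0.60 × 30 = 18, and 3 responders would give 16.7% instead of 10.0%.

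**6. Precision on a smaller denominator.** The formula in step 1 gives 20.0% at n = 24, 23.1% at n = 18, 25.3% at n = 15 and 28.3% at n = 12.

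**The case against.** Dividing by all patients is a legitimate, conservative choice. Read plainly, it already keeps patients who died, progressed or were not scanned in the denominator as non-responders. That stands, and it is why the all-patient rate should be kept. What is missing is a defined rate among patients who can respond, and a written rule for a zero baseline.

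Results are also stratified by radical resection versus biopsy, which will expose part of the effect. It does not settle the matter, because a surgical label is not the same as a lesion-free baseline scan, and strata do not define who is evaluable for response.

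A reader might infer more than the documents support on four points.

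- *That the protocol and the SAP use different denominators.* Protocol 12.3.2 matches the SAP; only Protocol 5.2 differs. Its extra words fit the schedule of analyses at week 52 and every 52 weeks after, so they most naturally say when ORR is calculated. The figure in step 5 rests on a strained reading.
- *That every fully resected patient is unable to respond.* The No Change rule covers only "patients who have undergone gross total resection and show neither contrast-enhancing (index lesions) nor non-enhancing lesions". A resected patient with measurable enhancing disease on the baseline scan can respond.
- *That ORR will be inflated by counting lesion-free patients as CR.* The CR sentence leaves this open, but something must be present before it can disappear, and Protocol 9.3.5 points to No Change.
- *That ORR reflects surgery and not the drug.* Surgical mix scales the rate; it does not create responders under the Protocol 9.3.5 rule.

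It is also fair to say that little depends on ORR. It has no target, power or test, and the benefit rule uses only one-year survival (at least 21 of 30) and progression-free survival (at least 11 of 30).

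**Conclusion.** The point holds, with limited impact. Under the rules as written, patients with no measurable enhancing disease at baseline are admitted, cannot be CR or PR, and remain in the denominator. ORR is therefore multiplied by 1 − s. This rests on applying Protocol 9.3.5 to lesion-free patients and dividing by all 30. The share s is not in the documents; over an assumed 10% to 60% the factor runs from 0.9 to 0.4. The inflation route is a gap in the CR wording to close, not the expected result. The difference between Protocol 5.2 and the other two texts calls for harmonising and is not a demonstrated conflict over the denominator. No conclusion about benefit changes, because ORR is a descriptive secondary endpoint outside that rule.

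**What to change.** Put one ORR definition in Protocol 5.2, Protocol 12.3.2 and SAP 1.3.2:

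- At month 12 and every 12 months after, report (CR + PR) among enrolled patients with measurable enhancing disease on the baseline study scan, with its own n and an exact 95% interval. State what counts as measurable, since the text gives no threshold.
- Report the all-patient rate beside it.
- In both rates, count patients who died, progressed or were not scanned as non-responders. The last group will occur, because Protocol 9.3.4 leaves the study scan to the investigator's discretion when treatment stops for avelumab-related events or clinical progression.
- Report patients without measurable baseline disease separately, as recurrence-free or not, and state that they are never scored CR.

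The baseline scans are already required, so no procedure is added. The cost is precision: the worst-case margin for the measurable-disease rate would be about 20% at n = 24 or 25% at n = 15 (both assumed sizes). The sample size section should therefore say that its margin of under 18% applies to rates on all 30 patients and not to this one.

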### **5.3. Exploratory**

The correlation between OS and PFS and the prevalence of PD-L1 expression on tumor cells and microglia/macrophages within the tumor, the histological immunoscore.

The correlation between OS and PFS and the baseline corticosteroid dose, the total cumulative corticosteroid dose over the whole study duration, the total cumulative dose of temozolomide since diagnosis, the baseline value and the change from baseline to week 52 visit and/or the end of study neurocognitive function as measured by the evoked potential P300 and the incidence and severity of irAE's.

The change between baseline biomarker results and those obtained from biomarkers in tissue samples from patients with second surgical resection i.e. treatment failures

The description of the time period in which radiological progression was seen in clinically stable patients whose imaging was subsequently followed by radiological stabilization or regression

The description of the time period in clinically stable patients before radiological evidence tumor regression occurred

The change in P300 evoked potential values and its correlation with clinical outcomes

**Safety monitoring:** There will be an internal DSMB which will make annual reviews.

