## **4. STUDY DESIGN**

### **4.1. Overview of Study Design**

This is a single center, phase 2, open label, open-ended, add-on, single dose study of maximum duration of 260 weeks in patients receiving standard therapy for newly diagnosed GBM. In total 30 patients who meet the entry criteria will be entered into the study within 3 weeks of finishing their last day of combined radiotherapy/temozolomide. Avelumab will be initiated concurrently with the initiation of the first 5 days, monthly cycle of temozolomide.

The study will consist of 3 different phases: Combination Phase a Monotherapy Phase and an Extended Safety Follow-up Phase.

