#### **4.4. Number of Subjects**

A total of 30 patients will be recruited.

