1.3.3. Exploratory

The incidence of PD-L1 expression on tumor cells and microglia/macrophages within the tumor will be determined and correlated to OS and PFS and other iRANO endpoints

The histological immunoscore will be determined and tested for association with OS, PFS, and other iRANO endpoints using logistic regression.

The association between 12 months OS and PFS with baseline neurocognitive function as measured by the evoked potential P300 (normal), the baseline corticosteroid dose, the average daily corticosteroid dose over the whole study duration, the extent to which patients complete the full 6 cycles of temozolomide based on temozolomide toxicity and the incidence and severity of treatment related irAE's will be tested using logistic regression.

The change if any in histological markers on tissue obtained from repeat resection

The estimation of the time period in which radiological progression was seen in clinically stable patients whose imaging was subsequently followed by radiological stabilization or regression

The estimation of the time period in clinically stable patients before radiological evidence of tumor regression occurred

The change in P300 will be determined and correlated with clinical outcomes as per iRAN

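### On-study steroid dose is defined in two ways, and each whole-study measure can create a spurious association with OS and PFS

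*Protocol*

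**What the plan says.** Five places in the protocol name the summed dose: the synopsis three times (exploratory objectives, exploratory endpoints, tertiary endpoints), section 3.3 and section 5.3. The wording in 5.3 is "the total cumulative corticosteroid dose over the whole study duration", to be correlated with OS and PFS.

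Two places name a daily average: Protocol 12.3.3 and SAP 1.3.3, which match each other. The SAP wording is "the average daily corticosteroid dose over the whole study duration". These sections also change the form of the outcome and name a method: "The association between 12 months OS and PFS with baseline neurocognitive function" and the other listed predictors, ending with "severity of treatment related irAE's will be tested using logistic regression".

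OS "will be defined as the time from baseline to the date of death from any cause" (Protocol 5.2). Protocol 4.1 describes a "single dose study of maximum duration of 260 weeks", so follow-up can differ several-fold between patients. Neither document sets an exposure window, a landmark or a time-varying analysis for steroid dose.

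Three other provisions bear on the point. Protocol 8.4 asks investigators to taper dexamethasone as symptoms allow. Inclusion criterion 5 caps the entry dose. Protocol 8.1 requires concomitant drugs on the CRF only up to the safety follow-up visit.

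**The concern.** Cumulative dose is average daily dose multiplied by time observed, so the two measures answer different questions, and an analyst could follow either and be within the plan. The choice could be made after the data are seen.

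The larger problem is that both measures contain the outcome. A patient who lives longer has more time to accumulate steroid, and also has a longer period over which an early course is averaged. For the 12-month outcome in the statistical sections, a whole-study measure also lets dosing after month 12 help predict status at month 12. The complete analysis is repeated every 52 weeks, so the cumulative measure can keep growing among survivors from one report to the next.

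What is at stake is the reported direction of the link between steroid use and survival on an immunotherapy, which readers will look for even in an exploratory table.

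**Working it through.** The plan gives no figure on this point, so there is none to reproduce.

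**Algebra.** Let *d* be the daily dose while on steroids, *u* the time on steroids and *F* the follow-up time. Cumulative = *d* × min(*u*, *F*). Average = cumulative / *F*. Take two patients on the same *d*, followed for 6 and 24 months.
- Constant use: cumulative 6*d* and 24*d*; average *d* and *d*.
- Use in the first 3 months only: cumulative 3*d* and 3*d*; average 3*d*/6 = 0.5*d* and 3*d*/24 = 0.125*d*.

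The distortion falls on the cumulative measure in the first case and on the average in the second.

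**Inputs from the documents.** n = 30 ("A total of 30 patients will be recruited", Protocol 4.4). Reference rates: "one-year overall survival and progression-free survival rates of 60% and 27%, respectively" (SAP 1.3.2).

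**Assumptions.** Exponential survival; log-normal daily dose with SD 0.7 on the log scale; follow-up cut at 3 years; steroid use either constant or limited to the first 3 months; none or half of the patients never on steroids; dose either without effect or harmful with a log-hazard ratio of 0.8 per SD of log dose.

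**Method.** Yearly hazard = -ln(0.60) × exp(βz) = 0.511 × exp(βz), with z the standardised log dose. The statistic is the Spearman correlation with survival beyond one year. It is called significant if |r| × √29 > 1.96, that is |r| > 0.364.

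| Assumed use | True effect of dose | Cumulative, mean r | Average, mean r |
|---|---|---|---|
| Constant, all on steroids | none | +0.69 | 0.00 |
| Constant, all on steroids | harmful | +0.65 | -0.43 |
| Constant, half never on steroids | none | +0.18 | 0.00 |
| First 3 months, all on steroids | none | +0.13 | -0.68 |
| First 3 months, all on steroids | harmful | -0.22 | -0.79 |
| First 3 months, half never on steroids | none | about +0.04 | about -0.2 |

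In the first row cumulative dose is significantly beneficial in over 99% of trials. In the fourth row average dose is significantly harmful in 99% of trials. Dose has no effect in either row.

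**Check with survival time as the outcome**, follow-up cut at 60 months, log-SD 0.5 or 1.0, doses capped at 12 mg, no dose effect, all on steroids. Constant use: cumulative +0.89 or +0.75, average 0.00. First 3 months only: cumulative +0.15 to +0.20, average -0.72 to -0.87. The pattern is the same.

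**Early window with a 3-month landmark.** Every patient in the analysis then has the same exposure time, so cumulative and average dose differ only by a constant and rank patients identically. The mean no-effect correlation is 0.00 (range -0.01 to +0.01) under constant and 3-month use, at both the OS and the PFS reference rates. At a hazard ratio of 1.5 per SD it is -0.20 to -0.30, so a real association still shows with its own sign.

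**Patients lost at the landmark.** OS: 0.60^(3/12) = 0.880, so 12% of 30, or 3.6 patients. PFS: 0.27^(3/12) = 0.721, so 28%, or 8.4 patients.

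**The case against.** The strongest reply is that the statistical sections of both documents agree on average daily dose and name logistic regression on 12-month status. The objectives and endpoints could then be read as loose wording that gives way to them. The analysis is exploratory, and the study has 30 patients and is mainly descriptive. The benefit rule in SAP 1.3.2 does not use steroid dose. The simulated dosing patterns are not in the documents, and the table pairs the cumulative measure with a 12-month outcome that section 5.3 does not specify.

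Much of this stands, and it sets the severity. The pairing matters little, because the check with survival time gives the same pattern. Precedence is not stated anywhere, and choosing the average does not cure the defect, as the 3-month rows show.

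A reader might infer three stronger conclusions that the documents do not support.
- That cumulative dose must come out positive whatever the truth. This needs near-universal steroid use that continues throughout follow-up. Protocol 8.4 asks for taper, and inclusion criterion 5 sets a ceiling without requiring steroid use. With half of patients never on steroids and a harmful effect (non-users given a log-hazard of -0.8), cumulative dose averages -0.04.
- That the two measures give opposite answers. Under constant dosing with no effect the average is null, not opposite; under early taper with true harm both are negative.
- That this is protocol against SAP, with the SAP right. Protocol 12.3.3 already carries the SAP's measure, and that measure can itself show harm where there is none.

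**Conclusion.** The inconsistency is certain from the text: five places against two, with the split inside the protocol. It is also certain by algebra that both measures depend on follow-up time and that nothing in the plan removes this.

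The size of the bias is conditional. With no true effect, cumulative dose is pushed upward by anything from about +0.04 to +0.69 on the rank correlation with one-year survival. Average dose is pushed downward by about 0.2 to 0.7 if steroids stop early, and not at all if dosing is constant. These ranges rest on assumed duration of use, share of non-users, dose spread and exponential survival. They show direction and possible scale, and are not a forecast for this trial.

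Severity is low. The analysis is exploratory, and no primary or secondary conclusion changes. It is still worth correcting, because the plan as written allows either measure and either could manufacture an association.

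**What to change.** 1. Use one steroid measure in all seven places: the three synopsis entries, Protocol 3.3, 5.3 and 12.3.3, and SAP 1.3.3.
2. Keep baseline dose as a predictor. It is fixed before follow-up and has neither defect.
3. Relate on-study dose to OS and PFS in one of two ways, chosen in advance: dose over a pre-set early window (for example baseline to month 3) among patients still event-free at its end, with the outcome counted from that point; or dose as a time-varying covariate in a Cox model. For PFS the landmark is the safer choice. After the first 3 months, Protocol 8.4 can count a high or prolonged steroid requirement as progression, so a time-varying dose would overlap with the event.
4. Report whole-study total and average dose descriptively only, and do not correlate them with OS or PFS.

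The cost is wording in seven places and a short method statement. No new data are needed for an early window, since Protocol 8.1 already puts steroid dose, frequency and dates on the CRF. Because general recording stops at the safety follow-up visit, exposure up to death may not be available in any case. The price of the landmark is that patients with earlier events leave that one analysis: roughly 12% for OS and 28% for PFS at 3 months under the plan's reference rates. Their number should be reported beside the result.
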